## **Reporting Procedures for Unanticipated Problems**

Our research team will follow the guidelines described above and below for reporting unanticipated problems. The level of risk for the study and unanticipated problems will all be monitored and managed directly by the Project Investigator with support from the Project Director.

Consultation from the Brown IRB will be immediately available to the PI to address any required actions, investigations, or changes to the risk level of the study.

Events that satisfy any of the criteria for an unanticipated problem described above must be reported promptly to the Brown IRB and NIDA. Timelines for reporting unanticipated problems depend on the unanticipated problem category. Unanticipated problems that involve the loss of privacy or the loss of confidentiality will be reported to the IRB and NIDA within one business day of discovery. Unanticipated service disruption problems must be reported to the IRB and NIDA within 30 days of discovery. Unanticipated problems that involve changes to trial logistics must be reported to the IRB and NIDA within six months of discovery if the unanticipated problem is unresolved after three months of discovery. Unanticipated problems involving inappropriate access by criminal justice must be reported to the IRB within six months of discovery if the unanticipated problem is unresolved after three months.

The DSMB will be notified of any unanticipated problems and will be asked to convene at the earliest possible time to discuss, but no longer than 30 days after the unanticipated problem notification.

## **Plans for Interim Analysis of Efficacy Data**

Since the study outcomes for non-fatal and fatal overdoses in part rely on mortality data from the Office of the State Medical Examiner (OSME) that is delayed by approximately five months, detection of a significant difference between the intervention arm and the control arm may be unlikely within a brief time period. As such, one interim analysis for efficacy will be conducted 18 months after the launch of the trial. The DSMB will review these results and may decide to continue or terminate the trial if there is evidence of efficacy at 18 months.

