## **B. Analysis and Data Management**

### **Analysis:**

The analysis plan will be finalized and uploaded to the Open Science Framework (osf.io) before the start of the data analysis in accordance with the pre-specified analysis plan. We will employ standard methods for community intervention trials. The intervention effect will be quantified as a composite fatal and non-fatal overdose incidence rate ratio. We will have at least 5 years of data (from 2016 to 2020) to serve as the pre-intervention period. The trial formally began in November, 2021. We will exclude a six-month 'ramp up' period in all analyses to allow time for the targeted interventions to be deployed. We will have approximately two years of post-intervention data from May 15, 2022, to August 15, 2024.

We will use generalized linear mixed-effect modeling with Poisson or negative binomial link functions to estimate incidence rate ratios comparing overdose rates in treatment cities/towns to control cities/towns. Each municipality will have its own random intercept and slope to account for pre-intervention differences and time trends. Municipal population size will be incorporated as an offset, and 95% confidence intervals will be calculated using standard bootstrapping techniques to account for possible overdispersion of the data and the relatively small number of geographic units per arm. Although we will use stratified randomization to reduce pre-intervention differences in the treatment and control groups, potential biases from the imbalance can be corrected by including other covariates in the model. For example, measures of municipal-level racial/ethnic composition (e.g., percentage Hispanic/ Latino) will be included as covariates, given some evidence of imbalance in these variables between the two arms. Next, we will construct time-lagged regression models to consider the delayed impact of the interventions by staggering outcomes by zero to 6 months.

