## **E. Trial Stopping Rules**

The entire trial will stop if any investigator or a member of the DSMB judges it necessary for medical, safety, regulatory, or other reasons consistent with applicable laws, regulations, or good clinical practice. Once a concern of this proportion is raised, the decision to stop the trial will be made through immediate consultation with the IRB, the DSMB, and NIDA.

The trial may be stopped for the following reasons:

1. The occurrence of unanticipated events involving a loss of confidentiality or privacy (e.g., unintended or unauthorized access to the web tool housing model predictions or row-level data used as inputs for the predictive model).
2. The occurrence of unanticipated events involving a disruption to harm reduction service provision as a result of the study (e.g., diversion of resources away from cities/towns randomized to the control arm that would not have otherwise occurred if the study had not been taking place).
3. It becomes clear that successful completion of the study is not feasible due to logistical or administrative reasons (e.g., changes in leadership at the Rhode Island Department of Health, significant changes to the financial resources available to fund harm reduction service provision).
4. If factors external to the study fundamentally change the study's equipoise.
5. If the occurrence of an unanticipated event involves inappropriate access by criminal justice to the PROVIDENT model predictions or any information related to the trial that would not otherwise be granted.

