### **The content of the annual DSM report will include the following:**

- a. Brief description of the trial
- b. Summary of qualifying data events observed during the annual period (i.e., fatal and nonfatal overdoses) by study arm
- c. Regulatory issues
- d. Unanticipated problems (as described above)
- e. Efficacy of the trial interim analyses (conducted once at 18 months)

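### The 18-month efficacy look can end the trial with no boundary, significance level or data cut, and the final 95% interval takes no account of it

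*SAP*

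**What the plan says.** SAP section F, under Plans for Interim Analysis of Efficacy Data, states that "one interim analysis for efficacy will be conducted 18 months after the launch of the trial". The reason for a single, late look is that the outcome depends partly on "mortality data from the Office of the State Medical Examiner (OSME) that is delayed by approximately five months". The decision rule is one sentence: "The DSMB will review these results and may decide to continue or terminate the trial if there is evidence of efficacy at 18 months".

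Nothing else in the documents makes that rule numerical. SAP section B (Analysis) describes a mixed model with bootstrap 95% intervals and does not mention the look; nor does the power section. The five reasons listed in SAP section E after "The trial may be stopped for the following reasons" do not include efficacy. Protocol question 17 sends the reader to this same plan for the stopping rules.

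Two related statements bear on who sees what, and when. The annual monitoring report is to contain a "Summary of qualifying data events observed during the annual period (i.e., fatal and nonfatal overdoses) by study arm" and the interim efficacy results. On the final analysis, section B says: "The analysis plan will be finalized and uploaded to the Open Science Framework (osf.io) before the start of the data analysis".

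**The concern.** A look that can end the trial for benefit gives a chance finding a second opportunity to be declared an effect. Unless the first test is made strict or the second is tightened, the overall false-positive rate exceeds the level that a 95% interval implies. Here the first test is not defined at all, so the error rate cannot be stated.

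The second issue is what the look would contain. Deaths arrive about five months late and six months of ramp-up are excluded, so an analysis run at 18 months has little mature mortality data. The plan does not say at which date each part of the composite would be cut. An early stop could therefore end a statewide trial on a small share of its deaths, under a criterion that nobody could later reconstruct.

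**Working it through.** **The plan's own figure.** The SAP claims at least 95% power for a reduction above 25% with one year of follow-up. I used 5,000 stratified 1:1 allocations of the 39 municipalities, the Table S1 totals (1,461 + 336 = 1,797 events in 1,052,567 people) and a two-sided 0.05 Poisson comparison. The minimum power at a 25% reduction is 99.9%, so the claim is met as a floor. That calculation includes neither an interim look nor between-town variation.

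**Maturity at the look.** Inputs are from SAP sections B and F.
- Launch: "The trial formally began in November, 2021". The day is not given; 15 November is implied by the 15 May 2022 start of follow-up less six months.
- Look: 15 November 2021 + 18 months = 15 May 2023.
- Deaths complete to: 15 May 2023 − 5 months = 15 December 2022.
- Mature deaths: 15 May to 15 December 2022 = 7 months (6.5 to 7.5 for a launch on any day of November).
- Full follow-up: 15 May 2022 to 15 August 2024 = 27 months. 7/27 = 26%.

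**Expected events at the 2016 rates.**
- Full follow-up: 1,797 × 27/12 = 4,043.
- Both components cut at 7 months: 1,797 × 7/12 = 1,048, or 26%.
- Non-fatal events current to 12 months, deaths to 7: 1,461 + 336 × 7/12 = 1,657, or 41%.
- Analysis delayed until 12 months of deaths are in: 12/27 = 44%.
- Deaths alone: 336 × 7/12 = 196 of 336 × 27/12 = 756. Deaths are 336/1,797 = 18.7% of the composite.

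**Overall type I error.** The interim and final statistics are treated as bivariate normal with correlation √t, where t is the information fraction. The error is 1 − P(|Z1| < c1, |Z2| < c2). The 0.05 level is assumed; 3.29 corresponds to two-sided p = 0.001.

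| t | both looks at 0.05 (c1 = c2 = 1.96) | p<0.001, then 0.05 (c1 = 3.29, c2 = 1.96) |
|---|---|---|
| 7/27 = 0.26 | 9.05% | 5.06% |
| 0.41 | 8.60% | 5.03% |
| 12/27 = 0.44 | 8.49% | 5.03% |
| 0.67 | 7.70% | 5.01% |
| 0.90 | 6.48% | 5.00% |

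The last two rows cover the case in which variation between towns dominates, so that further months add little information and the two looks are highly correlated. By symmetry, half of each figure lies in the direction of benefit (4.5% at t = 0.26, against 2.5%).

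**Other controlled rules, overall 0.05.** O'Brien-Fleming-type spending needs p<0.00012 at t = 0.26 or p<0.0022 at t = 0.41, leaving 0.0499 or 0.0491 for the final test. Equal levels would be 0.027 to 0.029 at each look.

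**The case against.** The strongest reply is that the SAP sets no 0.05 threshold. It leaves the decision to an independent board that includes a statistician and only permits a stop. A board could well demand far stronger evidence. That stands: a reader might infer that the trial as written has a 9% error rate, and the documents do not support so definite a statement. The figures describe one natural reading. Without a rule the error is undefined, which does not remove the gap.

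Several other inferences also go too far.
- **That the look rests on a quarter of the information.** The 7 of 27 months apply to deaths. The composite fraction is 26 to 41%, and calendar time is only a proxy for information in a model with random intercepts and slopes.
- **That the look would combine different windows for deaths and non-fatal events.** This is possible, not stated. The plan gives no cut, and no lag for non-fatal events.
- **That section E forbids an efficacy stop.** Its opening sentence allows stopping for other reasons, and section F of the same plan provides for this one. A cross-reference is missing; there is no contradiction.
- **That annual counts by arm compromise the model choices.** The SAP requires the analysis plan to be final before data analysis begins, and an efficacy look is data analysis. The team also receives the surveillance data every six months, so pooling the report would not blind it.

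It is also fair to say that a trial that passes the look has less to answer for. If both looks use 0.05, the chance of a false positive at the end, given continuation, is (0.0905 − 0.05)/0.95 = 4.3% at t = 0.26 and (0.0849 − 0.05)/0.95 = 3.7% at t = 0.44. The excess enters through an early stop.

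Finally, the look was due about May 2023. SAP section B discusses a Providence police change effective June 2023, and a protocol figure is dated March 2024. A boundary written now cannot be presented as prespecified for a look already taken. This changes the remedy, not the finding.

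**Conclusion.** The concern holds. The SAP permits termination for efficacy at one look with no boundary, level or data cut, and the final interval is unadjusted. If both analyses are judged at two-sided 0.05, overall type I error is about 8.5 to 9.0% for fractions of 0.26 to 0.44, and about 6.5 to 7.7% for fractions of 0.90 to 0.67. It exceeds 5% at every fraction examined. Under another reading it cannot be calculated.

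The maturity figures assume a mid-November 2021 launch and an analysis actually run at 18 months; the event fractions assume 2016 rates. A boundary may be intended for the analysis plan still to be posted, but neither document says so. The documents also do not show whether the look took place.

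**What to change.** - **State a boundary.** One option is Haybittle-Peto: two-sided p<0.001 on the planned primary model at the single look, with the final test at 0.05. The overall error is then 5.0 to 5.1%. Alpha spending, as shown above, is an equivalent choice if the total must not exceed 5%. State the overall level and sidedness too.
- **State the data cut.** End both components at the last date with complete medical-examiner data.
- **Cross-reference** the rule in SAP section E.
- **If the look has already taken place,** report its date and data cut, the rule that the board applied, the decision, and who saw results by arm. Set the final level to account for the alpha spent: 0.05 can stand if the rule was as strict as p<0.001, whereas equal testing needs 0.027 to 0.029 at each look. If no numerical rule was used, say so and do not present a boundary written afterwards as prespecified.
- **Lock and post the analysis plan** before any further efficacy analysis by arm.

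The cost is wording, plus a short factual account if the look has happened. The loss of final power is negligible. The drawback is that an early stop for benefit becomes harder.

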## **G. DSM Plan for Administration**

### **Responsibility for Data and Safety Monitoring**

The Principal Investigator, [name] [name], is responsible for data safety and monitoring. This process will be monitored weekly by his team, including the Project Director, Data Analyst, and Research Assistant, with quarterly updates to the entire team of Co-Investigators. The project team will ensure that all policies and processes outlined in the Data Use Agreements are followed accordingly and that data are transferred and shared on the agreed-upon timeline using the IRB-approved data transfer methods. Additional data and safety monitoring reporting includes semi-annual updates to the DSMB and annual reports to the IRB and NIDA.

### **The content of the annual DSM report will include the following:**

- a. Brief description of the trial
- b. Summary of qualifying data events observed during the annual period (i.e., fatal and nonfatal overdoses) by study arm
- c. Regulatory issues
- d. Unanticipated problems (as described above)
- e. Efficacy of the trial interim analyses (conducted once at 18 months)

## **Data and Safety Monitoring Board (DSMB) Plan**

## **Members and Affiliation, Conflict of Interest**

A single Data and Safety Monitoring Board (DSMB) will be appointed to oversee this project. The DSMB will consist of members outside the research group conducting this study but may include individuals affiliated with one or more data-sharing partners who are not directly related to the project. The DSMB will include at least one individual with expertise in statistics or biostatistics. Any potential conflicts of interest must be disclosed during the application process. The Brown University IRB will ultimately approve the membership, meeting frequency, and Safety Monitoring Plan for the DSMB.

## **Frequency of Meetings & Protection of Confidentiality**

The DSMB will meet semi-annually with the Co-PIs and project director to review DSMP protocol adherence. All Data Safety Monitoring Board members will receive a copy of the protocol. The protocol includes the data and safety monitoring plan, which will be used as a guide during the DSMB meetings. The DSMB will review any issues related to deviations from the protocol and reported unanticipated events. The DSMB will review and approve the study protocol before the start of the study and review major amendments to the protocol.

## **Monitoring Activities (initial and ongoing study review)**

Monitoring activities and stopping rules are specific to the scope of the PROVIDENT trial. While the PROVIDENT trial does not involve direct interaction with individuals receiving harm reduction services, it does change the environment in which these services are provided. As such, responsibilities will include monitoring the overall safety of these environmental changes to ensure the safety of the individuals receiving these harm reduction services.

Activities will include monitoring unanticipated problems that are:

1. Unexpected given the study protocols;
2. Related (or possibly related) to participation in the study; and
3. Suggested that the research places subjects or others at greater risk of harm than was previously recognized.

The DSMB will be notified within 24 hrs. of unanticipated problems that involve loss of privacy or breach of confidentiality. Upon notification of any unanticipated problem, the DSMB will convene at the earliest possible time to discuss it, but no longer than 30 days from the time of the unanticipated event notification. At the end of each meeting, the DSMB will vote on the continuation of the study, particularly regarding safety and confidentiality issues. The DSMB will also provide written reports to be shared with the IRB, summarizing oversight activities, recommendations, and any concerns regarding study safety.

The DSMB will provide this recommendation to the Co-PIs and IRB through study comments. In addition, the DSMB will determine if there is sufficient concern to stop the trial.

## **Communication Plan to IRB, NIDA**

The Principal Investigator and the Project Director will coordinate all communication and grant reporting to the necessary parties, with the goal of transparency across oversight boards (IRB, DSMB) and the funding institution. Examples of communication the PI shares include annual progress reports to NIDA, annual IRB protocol recertification, and semi-annual DSMB updates. Any unanticipated problems will be reported by the PI to the DSMB and IRB and, if required, the program officer at NIDA. The results of any DSMB or IRB comments will be shared as needed.

The DSMB will be asked to provide written documentation confirming a review of the protocol and agreement with the study design and the data safety monitoring plan (DSMP). The DSMB will ensure that all unanticipated problems are reported to the IRB by the Project Investigator according to policies and procedures.
